Primary: To estimate the percentage of patients progressing at 6 months by RECIST1.1 when maintained on a combination regimen of paricalcitol plus pembrolizumab versus pembrolizumab alone.

Secondary:

1. Evaluate the toxicity of the combination of paricalcitol plus pembrolizumab versus pembrolizumab alone.
2. Evaluate the difference in overall survival (OS) in patients administered the combination of paricalcitol plus pembrolizumab versus pembrolizumab alone.
3. Define the impact of the combination of paricalcitol and pembrolizumab on tumor mutational landscape and transcriptional programs.
4. Identify cellular VDR targets in the immune microenvironment with PD1 blockade.

Exploratory:

1. Evaluate the difference in disease progression according to iRECIST vs. RECIST 1.1 criteria (Appendix 5)
2. Assess the utility of a Patient Personalized Clinical Benefit (PPCB) phone-based

| |
|---|
| 
application
 
 3. Assess the association between improvement in symptoms as recorded by the Patient Personalized Clinical Benefit (PPCB) with progression at 6 months by RECIST 1.1 4. Assess any changes in tumor and/or tissue texture on imaging in both arms of the trial 5. To monitor and compare the gut microbial communities in both arms of the trial. |
| 
Trial Design: Randomized Double Blind, Placebo Controlled
 |
| 
No. Patients: Total of 24, 12 randomized to each treatment arm
 |
| 
Name, dose of drugs:
 
 • Pembrolizumab (Keytruda®) 200 mg administered as an intravenous infusion over 30 minutes every 3 weeks. • Paricalcitol (Zemlar®) 25 mcg administered intravenously 3 times per week (given on days 1, 3, 5, 8, 10, 12, 15, 17, 19 ± 1 day of each 21 day cycle) and prior to each pembrolizumab infusion. • Placebo- equivalent volume administered intravenously, 3 times per week and prior to each pembrolizumab infusion. |
| 
Treatment Arms: Arm1: pembrolizumab + paricalcitol Arm 2: pembrolizumab + placebo (saline solution)
 |
| 
Patient Population: Patients with stage IV pancreatic cancer who have been put in best response, defined as: Must have obtained a best response of at least stable disease (SD) or partial response (PR) for a period of 2 months with no further shrinkage of ≥ 30% on scan.
 |

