4.3 Randomization or Treatment Allocation

Randomization will be in a 1:1 ratio to pembrolizumab + paricalcitol or pembrolizumab + placebo. Randomization will be performed by the trial biostatistician or designee using a computer-generated algorithm with a block size of 4. The RAND function in MySQL is used to generate a random number, with a value based on the computer clock used as seed. The program randomly assigns participants to one of the two treatments with the pre-selected block size. After study initiation, the randomization sequence will be provided to the unblinded central monitor. After consent and confirmation of eligibility, the site study coordinator will notify the site pharmacist and the unblinded monitor. The unblinded monitor will provide the next randomized treatment from the sequence to the site pharmacist. The unblinded monitor also will notify the trial biostatistician. The trial biostatistician or designee will be available to assist with identifying the next randomized treatment if the unblinded central monitor is not available.

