8.3.5.3 Analysis of Tumor Mutational Landscape and Transcriptional Programs

The change in the biomarkers in the pre- versus 6-week biopsies will be estimated for each patient. A two-sample t test will be used to compare the continuous changes between the two treatment arms, assuming that the differences are normally distributed. If they are non-normal, a Wilcoxon Rank Sum Test will be used. A sensitivity analysis will use a linear regression model to compare the two treatment arms, adjusted for the baseline level.

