8.3.5.3 Analysis of Cellular VDR targets with PD1 Blockade

Analysis of the specified cellular VDR targets will be assessed using the change in the pre-versus 9-week biopsies. A two-sample t test or Wilcoxon Rank Sum Test, and a sensitivity analysis using linear regression will be performed as outlined previously.

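### Biomarker changes: baseline-adjusted regression should be the main comparison rather than a sensitivity analysis, if roughly 12 or more biopsy pairs are obtained

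*Protocol*

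**What the plan says.** Protocol 8.3.5.3 on the tumor mutational landscape and transcriptional programs sets the main test: "A two-sample t test will be used to compare the continuous changes between the two treatment arms, assuming that the differences are normally distributed". The fallback is also unadjusted: "If they are non-normal, a Wilcoxon Rank Sum Test will be used". Regression is ranked below both: "A sensitivity analysis will use a linear regression model to compare the two treatment arms, adjusted for the baseline level". The paragraph on cellular VDR targets, which carries the same section number, repeats the order: "A two-sample t test or Wilcoxon Rank Sum Test, and a sensitivity analysis using linear regression will be performed as outlined previously".

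These analyses serve secondary objectives 3 and 4 (Protocol 3.2). The SAP's title restricts it to clinical endpoints. It does not cover the biomarkers and so does not alter the order.

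The trial size is "Total of 24, 12 randomized to each treatment arm", which caps the number of pairs at 24. Fresh biopsies are optional (Protocol 4.1.1, criterion 5), and the repeat is taken only where possible (Protocol 6.1.2.8).

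**The concern.** Every patient in these comparisons has a baseline value, since no change can be computed without one. Subtracting baseline fixes its coefficient at 1. With equal SDs at the two visits the best coefficient is r. Unless r is close to 1, the change score over-corrects: a chance baseline difference d between arms shifts the estimated effect by −(1−r)d. Regression on arm and baseline estimates the coefficient and removes that shift on average.

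There is no stratification (Protocol 4.4), so sizeable imbalance is plausible. With 12 pairs, taken as 6 per arm, the SD of the baseline difference is √(2/6) = 0.58 marker SDs. At r = 0.5 an imbalance of that size moves the change-score estimate by 0.5 × 0.58 = 0.29 SD.

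What is at stake is which estimate is read as the main result for two secondary objectives, and how precise it is.

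**Working it through.** **Plan's own figure.** The documents give no power or precision for the biomarker analyses. The stated 90% power (Protocol 8.2) concerns the binary primary endpoint. It reproduces as 0.901 by enumeration for 1/12 versus 7/12, one-sided 0.05, 12 per arm, but has no bearing on this point.

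**Inputs.** From the documents: at most 24 pairs and randomised 1:1 allocation ("Randomization will be in a 1:1 ratio to pembrolizumab + paricalcitol or pembrolizumab + placebo"). Assumed, because not given: equal SD s at both visits, r from 0.3 to 0.9, N from 6 to 24 pairs in total, normal baseline values, a common linear slope.

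**Formulas.** Let k = 1/n₁ + 1/n₂ for the pairs in each arm.

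- Change score: variance = 2s²(1−r)k.
- Adjusted: variance = s²(1−r²)k × [1 + 1/(N−4)], where the bracket, equal to (N−3)/(N−4), is the average cost of estimating the slope.
- Ratio, adjusted to change score: (1+r)/2 × (N−3)/(N−4).
- Break-even, where the ratio is 1: r = (N−5)/(N−3).

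Example, N = 12 and r = 0.5: 0.75 × 9/8 = 0.84. Break-even at N = 12: 7/9 = 0.78.

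| Pairs N | Slope penalty | r = 0.3 | r = 0.5 | r = 0.7 | r = 0.9 | Break-even r |
|---|---|---|---|---|---|---|
| 24 | 5% | 0.68 | 0.79 | 0.89 | 1.00 | 0.90 |
| 16 | 8% | 0.70 | 0.81 | 0.92 | 1.03 | 0.85 |
| 12 | 12.5% | 0.73 | 0.84 | 0.96 | 1.07 | 0.78 |
| 8 | 25% | 0.81 | 0.94 | 1.06 | 1.19 | 0.60 |
| 6 | 50% | 0.98 | 1.13 | 1.28 | 1.43 | 0.33 |

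Below 1 favours the adjusted analysis.

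**Simulation check.** 40,000 trials per cell, with an assumed effect of 1.2 SD and two-sided 0.05, reproduced these ratios closely. Power, change-score t test versus adjusted regression:

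| Pairs N | r = 0.3 | r = 0.5 | r = 0.7 |
|---|---|---|---|
| 24 | 66% vs 82% | 80% vs 89% | 95% vs 97% |
| 12 | 36% vs 46% | 47% vs 53% | 68% vs 69% |
| 8 | 23% vs 27% | 29% vs 31% | 46% vs 43% |
| 6 | 16% vs 17% | 20% vs 19% | 31% vs 25% |

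At 12 pairs and r = 0.9 the figures are 99% and 98%, so the worst loss in this range at that size is small. At 6 pairs and r = 0.3, where the variances are almost equal, the average 95% interval from the regression is still 6% wider, because it also loses a degree of freedom.

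**The case against.** The adjusted regression is pre-specified, so its estimate will be produced under either order. A reader might infer that the plan discards the baseline information. It does not; the question is only which estimate is named as main.

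A reader might also infer that the change score wastes precision above all when biopsies are very few. The documents do not support that. They give neither r nor the number of pairs, and the formula points the other way: at 8 pairs the change score is the more precise once r exceeds 0.60, and at 6 pairs once it exceeds 0.33. With optional biopsies such numbers could occur. A straight line fitted to so few points also brings leverage and model assumptions that the t test and Wilcoxon test avoid.

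Under randomisation the change-score comparison is unbiased on average. Chance imbalance is a concern only conditionally on the baselines observed, and the planned sensitivity analysis would reveal it. No alpha, power or decision rule is attached to these endpoints.

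All of this stands, and it limits the weight of the point. It does not remove the gain at low to moderate r with 12 to 24 pairs, nor the value of fixing the better main estimate in advance. The present choice between t test and Wilcoxon rests on a normality judgement that a dozen pairs can hardly support.

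**Conclusion.** The point holds conditionally. With 12 to 24 pairs and r between 0.3 and 0.5, making the change score the main analysis forgoes a variance reduction of 16% to 32% (ratios 0.84 to 0.68). At r = 0.7 the reduction is 11% with 24 pairs and 4% with 12. A reader might take the gain to last until r is near 0.9; that is true only if all 24 patients give pairs. Below about 12 pairs the order matters little or favours the change score.

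These figures are a range under assumption, not an estimate. They rest on equal SDs at the two visits, a common linear slope, and patients with pairs remaining comparable between arms. Unequal SDs would change the ratios.

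Severity is minor and confidence moderate: the endpoints are secondary and unpowered, the adjusted estimate is already planned, and the primary result is untouched.

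**What to change.** In both paragraphs numbered 8.3.5.3:

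1. Make linear regression of the follow-up value (or the change) on arm and baseline the main analysis. For skewed markers use a log or rank scale within the same model. This replaces the data-driven switch of test in the main analysis.
2. Keep the change-score t test or Wilcoxon test as the sensitivity analysis.
3. Report both estimates with confidence intervals.
4. State in advance a minimum number of pairs, about 12, below which the comparison is descriptive.

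The cost is a change of order between two analyses already planned. The statistical price is one degree of freedom plus a slope-estimation penalty of 1/(N−4): 5% at 24 pairs, 12.5% at 12, 25% at 8 and 50% at 6. That growth is the reason for the minimum.

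Separately, the first paragraph refers to a 6-week biopsy, while the second and Protocol 6.1.2.8 refer to 9 weeks. The follow-up value cannot be defined until these are reconciled.

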8.3.5.3 Analysis of Cellular VDR targets with PD1 Blockade

Analysis of the specified cellular VDR targets will be assessed using the change in the pre-versus 9-week biopsies. A two-sample t test or Wilcoxon Rank Sum Test, and a sensitivity analysis using linear regression will be performed as outlined previously.

8.3.6 Analysis of Exploratory Endpoints

8.3.6.1 Comparison of RECIST 1.1 and iRECIST criteria

Given that pembrolizumab is an immunotherapy agent, disease progression will be defined by RECIST and iRECIST criteria (Appendix 5). Comparison of the proportion progression-free at 6 months using iRECIST will be performed using the same method as for the primary endpoint of RECIST 1.1. Additionally, McNemar's Test will be used to estimate the concordance between the two outcome measures.

8.3.6.2 Compliance to Use of a Phone-Based Application for Assessing Patient Defined Symptoms

The planned statistical analysis is included in Appendix 6.

8.3.6.3 Patient Personalized Clinical Benefit

The symptoms identified by each patient and the change across time will be evaluated graphically. The most severe ranking across the three items will be compared at baseline and the EOT visits to determine whether each patient's symptoms have improved across time. The relationship between progression at 6 months by RECIST 1.1 versus the change in rankings from baseline to EOT will be assessed using a Wilcoxon Rank Sum test.

8.3.6.4 Quantitative Textural Analysis (QTA)

The planned analysis for QTA is included in Appendix 7.

8.3.6.5 16S Gut Microbiome rRNA Analysis

The planned analysis for 16S Gut Microbiome is included in Appendix 8.

9.0 ADMINISTRATIVE AND REGULATORY DETAILS

9.1 Institutional Review Board/Ethics Committee Approval

Before trial initiation, this protocol and informed consent form will be submitted for review and approval to the IRBs charged with oversight for the clinical sites. In addition, any form of proposed advertising and advertising text for patient recruitment must be reviewed and approved by the Sponsor prior to submission to the IRB. The Investigator will forward to the Sponsor a copy of the IRB's approval of this protocol, any amendments, informed consent form, and any modifications to the informed consent, based on the FDA regulations set forth in 21 CFR 56 of the *Code of Federal Regulations*.

In addition, the Investigator will be responsible for forwarding to the Sponsor a description of the IRB members (including profession and affiliation) or a United States (US) Department of Health and Human Services (DHHS) General Assurance number and expiration date. If neither of these is available, the chairperson must submit a statement indicating that the members of the board responsible for the review meet the FDA and other appropriate regulatory requirements. In addition, the labeling for all approved trial medications should be submitted to the IRB for information purposes.

Clinical supplies will not be shipped to the clinical site until IRB approval is obtained for the protocol. Any existing amendments, informed consent, and photocopies of the approved documents must be received by the Sponsor prior to drug shipment.

9.2 Investigators protocol agreement

The Investigator must sign the Investigator's Protocol Agreement. The original must be kept on file by the Sponsor and the Investigator must retain a copy. The completed Investigator's Protocol Agreement signifies agreement to comply with all procedures outlined by this protocol by the Investigator. An Investigator's Protocol Agreement must be signed if and when a protocol amendment is issued.

9.3 Remaining Samples

Any samples remaining after the trial specified analyses is completed will be transferred to and stored at TGen if the patient consented for use of their remaining samples for future research purposes at TGen's discretion. This includes the original specimen collected from the patient [blood, tumor tissue, or fecal swabs]) as well as derivatives created from the original specimen (DNA, RNA, blocks or slides). Documentation of the transfer of all specimens will be recorded on the Sample Destruction/Return Request Form- refer to Trial Laboratory Manual.

If a patient has not consented for their remaining samples to be used for future research purposes, remaining samples and derivatives will be destroyed and documented on the Sample Destruction/Return Request Form- refer to Trial Laboratory Manual.

9.4 Confidentiality

The Investigator and any other personnel involved in this trial shall not disclose, or use for any purposes (other than for the performance of this trial any data, records, or other information (hereinafter collectively “information”) disclosed to the Investigator or other trial personnel. Such information shall remain the confidential and proprietary property of the TGen and SU2C, and shall be disclosed only to the Investigator or other designated trial personnel.

Patient confidentiality will be ensured by using assigned site-specific Screening and Randomization numbers (refer to Section 6.1) throughout the trial.

9.5 Publication

As a general rule, no trial results should be published without prior approval of the Sponsor. The rights of the investigator and the Sponsor with regard to publication of the results of this trial are described in the investigator contract.

9.6 Compliance with Financial Disclosure Requirements

All Investigators will be required to submit written financial disclosures to the Sponsor prior to participating in this clinical trial and any changes in disclosures during the course of the trial as per 21 CFR part 54.

9.7 Compliance with Trial Registration and Results Posting Requirements

Under the terms of the Food and Drug Administration Modernization Act (FDAMA) and the Food and Drug Administration Amendments Act (FDAAA), the Sponsor of the trial is solely responsible for determining whether the trial and its results are patient to the requirements for submission to the Clinical Trials Data Bank, <http://www.clinicaltrials.gov>. Information posted will allow patients to identify potentially appropriate trials for their disease conditions and pursue participation by calling a central contact number for further information on appropriate trial locations and trial site contact information.

9.8 Quality Management System

9.8.1 Data Monitoring Plan

Data monitoring procedures will be carried out by [REDACTED] for all participating sites, and will be performed on a regular basis to comply with Good Clinical Practice guidelines.

Review of the case report forms, cross-reference with source documents (including radiology review), review of trial related regulatory documents and logs (e.g. enrollment, trial site staff), would be monitored on an ongoing basis during monitoring sessions. The monitor will ensure that the investigation is conducted according to protocol design and regulatory requirements.

At the conclusion of the monitoring visit, the monitor will meet with the site staff to discuss and request specific corrections to the case report forms, and/or request clarification, and/or additional source documentation. The site Clinical Research Coordinator responsible for the trial will be provided with a copy of the written monitoring notes for resolution of the findings.

The monitor will complete a written monitoring report and provide to the Sponsor and [REDACTED]. The report will include a summary of what the site monitor reviewed and the site monitor's statements concerning the significant findings/facts, deviations and deficiencies, conclusions, actions taken or to be taken, and/or actions recommended to ensure compliance. The site Principal Investigator will be expected to submit any Corrective Action Plans, in writing, to the Sponsor. A copy of the monitoring forms, final monitoring reports, and Corrective Action Plan will be kept in the site monitor's trial file follow up at the next monitoring session.

For drug accountability an independent unblinded monitor will be assigned to monitor the Pharmacy file containing all information on preparation and dispensing of trial medication. Monitoring will occur on an ongoing basis to determine that the medication is being prepared and dispensed in accordance with the protocol design.

A *blinded* report documenting the visit and any findings will be written and provided to the Sponsor.

9.8.2 Data Safety Monitoring

A trial specific Data Safety Monitoring Plan (DSMP) will be implemented for this trial. The Trial Principal Investigators and an independent Medical Monitor will review the safety and progress of the trial on a regular interval and provide documentation of their review and any recommendations that will then be shared with the trial team.

The trial progress reports will be prepared by [REDACTED] in aggregate and provide blinded trial data pertaining to: patient recruitment, retention/attrition, data collection status, and adverse events. The progress reports will not provide data on the primary or secondary endpoints of the trial as there is no interim analysis planned for this trial.

In addition a separate unblinded trial report will be generated by the unblinded trial monitor and provided only to the independent medical monitor to review.

An annual trial progress report will be generated by [REDACTED] and sent to the Independent Monitor, Consulting Investigator, funding organization (SU2C), and each site Principal Investigator for submission to their governing IRB.

9.9 Data Management

9.9.1 Case Report Forms

All the clinical data will be captured by the site on electronic case report forms (eCRFs). The eCRFs will be used for all consented patients. The investigator and trained trial personnel will enter and edit the data via a secure network, with secure identification and

password requirement. A complete electronic audit trail will be maintained. The investigator will be required to provide approval of all data to confirm accuracy. Copies of the eCRFs will be provided to the investigator at the conclusion of the trial.

Appendix 1 - Pembrolizumab (Keytruda®) Package Insert

The pembrolizumab (Keytruda®) package insert can be accessed at the following link:

https://www.accessdata.fda.gov/drugsatfda_docs/label/2016/125514s012lbl.pdf

Appendix 2 - Paricalcitol (Zemplar®) Package Insert

The paricalcitol (Zemplar®) injection package insert can be accessed at the following link:

https://www.accessdata.fda.gov/drugsatfda_docs/label/2004/20819se5-014_zemplar_lbl.pdf

Appendix 3 - NCI CTCAE version 4.0

The CTCAE Version 4.0 can be accessed and downloaded from the CTEP website at:
https://ctep.cancer.gov/protocoldevelopment/electronic_applications/ctc.htm

Appendix 4 - ECOG Performance Status

| GRADE | ECOG PERFORMANCE STATUS |
|-------|---|
| 0 | Fully active, able to carry on all pre-disease performance without restriction |
| 1 | Restricted in physically strenuous activity but ambulatory and able to carry out work of a light or sedentary nature, e.g., light house work, office work |
| 2 | Ambulatory and capable of all self-care but unable to carry out any work activities; up and about more than 50% of waking hours |
| 3 | Capable of only limited self-care; confined to bed or chair more than 50% of waking hours |
| 4 | Completely disabled; cannot carry on any self-care; totally confined to bed or chair |
| 5 | Dead |

Appendix 5 - Protocol Criteria for Measurement of Trial Endpoint RECIST 1.1 and iRECIST

1. Definitions

- 1.1. Evaluable for adverse events. All patients will be evaluable for adverse event evaluation from the time of their first treatment.
- 1.2. Evaluable for response. All patients who have received at least one cycle of therapy and have their disease re-evaluated will be considered evaluable for response (exceptions will be those who exhibit objective disease progression prior to the end of cycle 1 who will also be considered evaluable). Patients on therapy for at least this period and who meet the other listed criteria will have their response classified according to the definitions set out below.

Response and progression will be evaluated in this study using the revised international criteria (1.1) proposed by the RECIST (Response Evaluation Criteria in Solid Tumours) committee as well as the modified iRECIST guidelines. Investigators should note the different requirements for confirmatory scans as well as follow up for the two criteria.

See section 6.1.2.6 for criteria for continuing treatment past RECIST 1.1 disease progression.

2. RECIST 1.1 Response and Evaluation Endpoints

- 2.1. Measurable Disease. Measurable tumour lesions (nodal, subcutaneous, lung parenchyma, solid organ metastases) are defined as those that can be accurately measured in at least one dimension (longest diameter to be recorded) as ≥ 20 mm with chest x-ray and as ≥ 10 mm with CT scan or clinical examination. Bone lesions are considered measurable only if assessed by CT scan and have an identifiable soft tissue component that meets these requirements (soft tissue component ≥ 10 mm by CT scan). Malignant lymph nodes must be ≥ 15 mm in the short axis to be considered measurable; only the short axis will be measured and followed. All tumour measurements must be recorded in millimetres (or decimal fractions of centimetres). Previously irradiated lesions are not considered measurable unless progression has been documented in the lesion.
- 2.2. Non-measurable Disease. All other lesions (or sites of disease), including small lesions are considered non-measurable disease. Bone lesions without a measurable soft tissue component, leptomeningeal disease, ascites, pleural/pericardial effusions, lymphangitis cutis/pulmonis, inflammatory breast disease, lymphangitic involvement of lung or skin and abdominal masses followed by clinical examination are all non-measurable. Lesions in previously irradiated areas are non-measurable, unless progression has been demonstrated.

2.3. Target Lesions. When more than one measurable tumour lesion is present at baseline all lesions up to a maximum of 5 lesions total (and a maximum of 2 lesions per organ) representative of all involved organs should be identified as target lesions and will be recorded and measured at baseline. Target lesions should be selected on the basis of their size (lesions with the longest diameter), be representative of all involved organs, but in addition should be those that lend themselves to reproducible repeated measurements. Note that pathological nodes must meet the criterion of a short axis of ≥ 15 mm by CT scan and only the short axis of these nodes will contribute to the baseline sum. All other pathological nodes (those with short axis ≥ 10 mm but < 15 mm) should be considered non-target lesions. Nodes that have a short axis < 10 mm are considered non-pathological and should not be recorded or followed (see 8.2.4). At baseline, the sum of the target lesions (longest diameter of tumour lesions plus short axis of lymph nodes: overall maximum of 5) is to be recorded.

After baseline, a value should be provided on the CRF for all identified target lesions for each assessment, even if very small. If extremely small and faint lesions cannot be accurately measured but are deemed to be present, a default value of 5 mm may be used. If lesions are too small to measure and indeed are believed to be absent, a default value of 0 mm may be used.

2.4. Non-target Lesions. All non-measurable lesions (or sites of disease) plus any measurable lesions over and above those listed as target lesions are considered non-target lesions. Measurements are not required but these lesions should be noted at baseline and should be followed as “present” or “absent”.

2.5. Response.

All patients will have their BEST RESPONSE from the start of study treatment until the end of treatment classified as outlined below:

Complete Response (CR): disappearance of target and non-target lesions and normalization of tumour markers. Pathological lymph nodes must have short axis measures < 10 mm (Note: continue to record the measurement even if < 10 mm and considered CR). Residual lesions (other than nodes < 10 mm) thought to be non-malignant should be further investigated (by cytology specialized imaging or other techniques as appropriate for individual cases⁴ before CR can be accepted. Confirmation of response is only required in non-randomised studies.

Partial Response (PR): at least a 30% decrease in the sum of measures (longest diameter for tumour lesions and short axis measure for nodes) of target lesions, taking as reference the baseline sum of diameters. Non target lesions must be non-PD. Confirmation of response is only required in non-randomised studies.

Stable Disease (SD): Neither sufficient shrinkage to qualify for PR nor sufficient increase to qualify for PD taking as reference the smallest sum of diameters on study.

Progressive Disease (PD): at least a 20% increase in the sum of diameters of measured lesions taking as references the smallest sum of diameters recorded on study (including baseline) AND an absolute increase of ≥ 5 mm. Appearance of new

lesions will also constitute progressive disease (including lesions in previously unassessed areas). In exceptional circumstances, unequivocal progression of non-target disease may be accepted as evidence of disease progression, where the overall tumour burden has increased sufficiently to merit discontinuation of treatment or where the tumour burden appears to have increased by at least 73% in volume. Modest increases in the size of one or more non-target lesions are NOT considered unequivocal progression. If the evidence of PD is equivocal (target or non-target), treatment may continue until the next assessment, but if confirmed, the earlier date must be used.

Table S1: Integration of target, non-target and new lesions into response assessment

| Target Lesions | Non-Target Lesions | New Lesions | Overall Response | Best Response for this Category also Requires |
|---|---------------------------|-------------|------------------|--|
| Target lesions ± non target lesions | | | | |
| CR | CR | No | CR | Normalization of tumour markers, tumour nodes <10 mm |
| CR | Non-CR/Non-PD | No | PR | |
| CR | Not all evaluated | No | PR | |
| PR | Non-PD/ not all evaluated | No | PR | Documented at least once ≥4 wks. from baseline |
| SD | Non-PD/ not all evaluated | No | SD | |
| Not all evaluated | Non-PD | No | NE | |
| PD | Any | Any | PD | |
| Any | PD | Any | PD | |
| Any | Any | Yes | PD | |
| Non target lesions ONLY | | | | |
| No Target | CR | No | CR | Normalization of tumour markers, tumour nodes <10 mm |
| No Target | Non-CR/non-PD | No | Non-CR/non-PD | |
| No Target | Not all evaluated | No | NE | |
| No Target | Unequivocal PD | Any | PD | |
| No Target | Any | Yes* | PD | |
| 
Note: Patients with a global deterioration of health status requiring discontinuation of treatment without objective evidence of disease progression at that time should be reported as “symptomatic deterioration”. This is a reason for stopping therapy, but is NOT objective PD. Every effort should be made to document the objective progression even after discontinuation of treatment.
 
*Investigators should record all new lesions; if the new lesion is felt to be equivocal, treatment may be continued pending further assessments – see table 2.
 | | | | |

3. iRECIST Response Assessment

Overall response will also be assessed using iRECIST. Immunotherapeutics may result in infiltration of immune cells leading to transient increase in the size in malignant lesions, or undetectable lesions becoming detectable. The criteria are identical to those

of RECIST 1.1 in many respects but have been adapted to account for instances where an increase in tumour burden, or the appearance of new lesions, does not reflect true tumour progression.

Key differences are described below. All responses defined using iRECIST criteria are designated with a prefix. iRECIST time-point and best overall responses will be recorded separately.

